(5) Patients with serious difficulties in communication or intellectual deficit that impedes the ability to understand the intervention.

Reasons for the participant to be discontinued from the study:

- (1) Withdrawal of informed consent.
- (2) Non-attendance at the study visits (≥ 2 nutritional interventions),
- (3) Exclusion criteria found after enrollment, and
- (4) Any serious adverse event during the intervention period (based on data safety monitoring).
- (5) Admission to dialysis

Figure 1. CONSORT Flow Diagram

Sample size calculation

For the calculation of sample size, the formula was used to compare means of independent samples. A size of 27 patients per group was estimated, considering an expected difference in the Glycated Hemoglobin percentage of 0.7 reported in a previous study (6).

Randomization

Randomization was performed using the simple method without replacement with sealed envelopes. Recruited individuals will be allocated into one of two groups:

- (1) Teleconsultation ($n = 26$)
- (2) Face to face consultation ($n = 27$)

DIETARY INTERVENTIONS

The teleconsultation group received nutritional therapy by video call in real time, with a monthly frequency for 4 months. The consultation includes the evaluation or reevaluation, diagnostic treatment and educational approach. Failure to attend more than two consultations is considered an exclusion criterion.

The Face to face consultation group, received nutritional therapy through face-to-face consultations in the hospital with a monthly frequency for 4 months. The consultation includes the evaluation or re-evaluation, diagnosis, treatment and educational approach. Failure to attend more than two consultations is considered an exclusion criterion.

DATA ANALYSIS PRINCIPLES

To determine the difference between the nutritional interventions, the following changes from the baseline (I1) to the end of the study (I6) will be determined as primary outcomes:

- (1) Renal function with de the determination of the changes in the estimated glomerular filtration rate (eGFR)
- (2) Glycemic control with the determination of the changes in the Hemoglobin A1c (HbA1c)

To evaluate the adherence to nutritional interventions were determined as secondary outcome:

- (1) Level of compliance, was assessed using a self-reported Likert scale. Being the score 10 = good adherence and the score 1 = poor adherence to treatment.

STUDY PROCEDURES

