Data collection

The following clinical/dietary information was obtained:

- Socio-demographic data (a questionnaire).
- Dietary habits: a 3-day food record.
- Vital signs: blood pressure.
- Anthropometric measures: weight, height, body mass index (BMI).
- Gastrointestinal symptoms: frequency and duration.

In the blood serum, we evaluated markers of glucose, and hemoglobin A1c; serum creatinine, urea, albúmin and blood biometry.

STATISTICAL ANALYSIS PLAN

Categorical variables are presented as numbers and percentages, and comparisons between groups were performed with the chi-square or Fisher exact test as appropriate. According to

the Shapiro–Wilk test for data distribution, continuous variables are summarized as the means \pm standard deviations (SD) if normally distributed or medians and interquartile ranges (25–75th) if non-normally distributed and were compared using Student’s t-test or the Mann–Whitney U test, respectively. For variables measured at multiple time points, repeated measures analysis of variance tests were used for the comparisons between groups. For the analysis of the interaction or intervening variables, a stratified statistical analysis will be carried out, using contingency tables and the Mantel-Haenszel method. All tests were two-tailed, and a p value less than 0.05 were considered significant. Statistical analysis and graphics were performed with IBM® SPSS® Statistics Ver. 22).

ETHICS APPROVAL AND CONSENT TO PARTICIPATE

The trial was conducted in accordance with the principles of the Declaration of Helsinki and the International Conference on Harmonization Guidelines for Good Clinical Practice. All patients gave their written informed consent before any study-related procedure. The study was approved by the local ethics committee (14 CEI 14 039 048), was prospectively registered in clinicaltrials.gov (NCT03344549). No funding was received to conduct this study. The clinical trial was carried out under the CONSORT guidelines.

Informed consent was obtained from all subjects. All methods were carried out in accordance with relevant guidelines and regulations. All experimental protocols were approved by the Institutional Review Board “Comité de ética en Investigación del OPD Hospital Civil de Guadalajara [name]”

CONSENT FOR PUBLICATION

REFERENCES

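### Interaction is assigned to contingency tables and Mantel-Haenszel, which test one common effect; no homogeneity test, group-by-covariate term, outcome or stratifier is named

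*Combined protocol and SAP*

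**What the plan says.** One sentence in the Statistical Analysis Plan section governs this analysis: "For the analysis of the interaction or intervening variables, a stratified statistical analysis will be carried out, using contingency tables and the Mantel-Haenszel method". It gives no outcome, no stratifying variable and no rule for turning a measurement into categories.

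The rest of that section does not fill the gap. Categorical variables get chi-square or Fisher tests, and continuous variables get a t-test or Mann-Whitney test. For repeated variables, "repeated measures analysis of variance tests were used for the comparisons between groups". None of these is described with a covariate. The significance rule is general: "All tests were two-tailed, and a p value less than 0.05 were considered significant".

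Under Data Analysis Principles, the primary outcomes are "changes in the estimated glomerular filtration rate (eGFR") and "Glycemic control with the determination of the changes in the Hemoglobin A1c (HbA1c"). The secondary outcome is a compliance score: "Being the score 10 = good adherence and the score 1 = poor adherence to treatment". The Randomization section describes simple allocation by sealed envelope to groups of 26 and 27, so the design supplies no default stratifier.

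**The concern.** The sentence sets two aims and gives both the same tool. If intervening variables means covariates to adjust for, Mantel-Haenszel is a reasonable choice for a categorical outcome. Interaction is a different question: does the effect of teleconsultation differ between, say, patients with higher and lower baseline eGFR? Mantel-Haenszel pools over strata and asks whether the common effect is zero. Followed as written, the plan gives no formal test and no interval for interaction.

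A Mantel-Haenszel p value taken as an interaction result, under the plan's 0.05 rule, can mislead in both directions. It tends to be small when the effect is the same everywhere and large when effects are opposite and cancel.

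The scale is a second problem. The primary outcomes are continuous and the compliance score runs from 1 to 10, so none is in table form as defined. If the sentence is meant to cover them, the cut-point, the outcome and the strata all remain to be chosen, possibly after the data have been seen.

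**Working it through.** **1. What the method tests: a worked table.** The responder counts are hypothetical. The stratum sizes fit the 26 and 27 allocated.

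| Stratum | Teleconsultation | Face to face | Odds ratio |
|---|---|---|---|
| A | 9/13 | 4/13 | (9×9)/(4×4) = 5.06 |
| B | 4/13 | 9/14 | (4×5)/(9×9) = 0.25 |

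- Pooled Mantel-Haenszel odds ratio = (81/26 + 20/27) / (16/26 + 81/27) = 3.856/3.615 = 1.07.
- Test: observed 13, expected 13×13/26 + 13×13/27 = 12.76, variance 1.690 + 1.748 = 3.438. Chi-square = (13 − 12.76)²/3.438 = 0.017, p = 0.90.
- Breslow-Day homogeneity test (Tarone form) on the same tables: p = 0.009.

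The effects are opposite, and the planned test shows nothing.

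**2. An SD for the illustration.** The Sample size calculation section says: "A size of 27 patients per group was estimated, considering an expected difference in the Glycated Hemoglobin percentage of 0.7". It states neither SD nor power, so 27 cannot be reproduced without an assumption. Solving n = 2·SD²·(z₁+z₂)²/0.7² for n = 27, two-sided 5%:

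- 80% power: SD = 0.7 × √(27/2) / (1.960 + 0.842) = 0.918
- 90% power: SD = 0.793

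SDs of 1.2 and 1.5 are added as a pure sensitivity range.

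**3. Rejection rates on HbA1c change.** Assumptions: SD 0.918, normal outcomes, strata of 13 vs 13 and 13 vs 14, median split for the tables, two-sided 5%, 20,000 simulated trials per scenario. Power of the interaction term is exact, for the unadjusted change score.

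| True effect in the two strata | Mantel-Haenszel | Breslow-Day | Interaction term |
|---|---|---|---|
| 0.7 and 0.7 (no interaction) | 56% | 5% | 5% |
| 0.7 and 0 | 15% | 22% | 27% |
| +0.7 and −0.7 (extreme) | 2–4% | 59% | 78% |

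The 2–4% spans Mantel-Haenszel with and without continuity correction.

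**4. Same check with assumed response rates** (4,000 runs each), needing no SD or cut-point:

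| Response rates, teleconsultation vs face to face | Mantel-Haenszel | Breslow-Day |
|---|---|---|
| 0.7 vs 0.3 in both strata | 86% | 5% |
| 0.7 vs 0.3, and reversed | 4% | 86% |
| 0.7 vs 0.3, and 0.5 vs 0.5 | 30% | 32% |

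**5. What a correct analysis can achieve here.** The 95% CI half-width for the interaction is t(0.975, 49 df) × SD × √(3/13 + 1/14). At SD 0.918 this is 2.010 × 0.918 × 0.550 = 1.01 HbA1c points.

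| Assumed SD | Power, +0.7/−0.7 | Power, 0.7/0 | CI half-width |
|---|---|---|---|
| 0.793 | 88% | 35% | 0.88 |
| 0.918 | 78% | 27% | 1.01 |
| 1.2 | 55% | 18% | 1.33 |
| 1.5 | 38% | 13% | 1.66 |

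**The case against.** The best defence is that the sentence describes the familiar two-step stratified analysis: look at the stratum tables for effect modification, then pool by Mantel-Haenszel. On that reading it is incomplete rather than wrong, and the harm needs a misreading that the plan does not announce. No primary comparison depends on it. The simulation rests on an SD, strata and a median split that the plan does not contain. The large contrast comes from full reversal; for 0.7 versus 0 the gain from homogeneity test to interaction term is only 22% to 27%. The document is dated 30 October 2022 and partly in the past tense, so prespecification may no longer be possible.

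Much of this stands. Stratum tables can show heterogeneity informally, Mantel-Haenszel suits part of the sentence, the main comparisons are untouched, and the figures are illustrative. The power figures also leave out the baseline adjustment recommended below. But inspecting tables is neither a test nor an interval, and the sentence names interaction as a question to be analysed. The worked table makes the point without any SD. Low power is a reason to report an interval, not a p value that answers another question. If the data are already in hand, the stratifiers must be reported as chosen afterwards.

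The phrase intervening variables is itself ambiguous: it can mean a baseline confounder or something on the pathway after randomisation. The plan should say which.

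**Conclusion.** The concern holds. For interaction, the named method does not answer the stated question, and nothing elsewhere in the document supplies a homogeneity test, a group-by-covariate term, an outcome, a stratifier or a cut-point. That conclusion follows from what Mantel-Haenszel estimates and needs no assumed figures.

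The size does depend on assumptions. With SD 0.918, two equal strata and a median split, Mantel-Haenszel rejects in 56% of trials with no interaction and in 2 to 4% with complete reversal. The point should be corrected, but it concerns a supporting analysis and leaves the main comparisons of eGFR and HbA1c intact. With 53 patients, a moderate interaction would usually be missed by any method.

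**What to change.** State the outcome, the stratifiers and the test.

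- **Continuous primary outcomes:** fit a linear model of the end-of-study value on group, baseline value, a baseline stratifier and the group-by-stratifier term. Use a short list, for example baseline eGFR or stage, and baseline HbA1c. Report the interaction estimate with its 95% CI, labelled exploratory.
- **Categorical outcomes:** keep Mantel-Haenszel for adjustment and add a Breslow-Day homogeneity test where interaction is the question. If only such outcomes are meant, saying so and adding this test is the minimum repair.
- **Intervening variables:** define the term, and do not stratify on post-randomisation variables such as compliance.
- **Timing:** if outcome data have already been seen, say that the stratifiers were chosen afterwards.

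The cost is SAP wording and a small amount of analysis; no new data are needed. The estimates will be imprecise and cannot support a claim that no interaction exists.

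### For interacting or intervening variables the SAP names only contingency tables with Mantel-Haenszel, which cannot take the two continuous primary outcomes unless they are first cut at an unstated point

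*Combined protocol and SAP*

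**What the plan says.** The Data Analysis Principles section defines two primary outcomes as changes from baseline to study end: "Renal function with de the determination of the changes in the estimated glomerular filtration rate (eGFR") and "Glycemic control with the determination of the changes in the Hemoglobin A1c (HbA1c"). The secondary outcome is a self-reported compliance score: "Being the score 10 = good adherence and the score 1 = poor adherence to treatment". No section defines a responder, a threshold or a categorised form of any of these.

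The Statistical Analysis Plan section compares continuous variables between groups by t-test or Mann-Whitney, categorical variables by chi-square or Fisher, and variables measured repeatedly by repeated-measures ANOVA. None of these is described with a covariate. For interacting or intervening variables the one method given is that "a stratified statistical analysis will be carried out, using contingency tables and the Mantel-Haenszel method". The variables that would form the strata are not listed, and no regression or ANCOVA is named.

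The Sample Size Calculation section works on means: "the formula was used to compare means of independent samples", "considering an expected difference in the Glycated Hemoglobin percentage of 0.7 reported in a previous study".

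**The concern.** A contingency table needs categories, and neither primary outcome has any. To apply the stated method to change in HbA1c or eGFR, the analyst must choose a threshold. The plan offers neither a threshold nor a reason for one, so it could be chosen after the data are seen. A continuous stratifying variable would also have to be cut.

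Two things are at stake. The stratified comparison of teleconsultation with face-to-face consultation would estimate an odds ratio, while the trial was sized and is mainly analysed on a difference in means. And with 53 patients, discarding the size of each patient's change can cost substantial power, so a null stratified result might reflect the cut and not the variable being examined.

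**Working it through.** **Inputs from the documents**
- Difference 0.7 HbA1c points and 27 per group (Sample Size Calculation).
- Allocation 26 and 27 (Randomization).
- Test level: "All tests were two-tailed, and a p value less than 0.05 were considered significant" (Statistical Analysis Plan).

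**Assumed, because not stated:** planned power 80% or 90%, and a normally distributed HbA1c change.

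**Step 1. The plan's own figure.** The 27 per group cannot be reproduced without an SD and a power, but the formula for two means can be inverted. From n = 2(z₀.₉₇₅ + z_power)² SD² / 0.7², SD² = 27 × 0.49 / [2(1.960 + z_power)²].
- 80% power: 13.23 / (2 × 7.849) = 0.843, so SD = 0.918 and d = 0.7/0.918 = 0.762.
- 90% power: 13.23 / (2 × 10.507) = 0.630, so SD = 0.793 and d = 0.7/0.793 = 0.882.

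The exact t calculation gives nearly the same: SD 0.90 (d = 0.777) and 0.78 (d = 0.899).

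**Step 2. Closed-form loss at the midpoint, 27 per group.** The proportions beyond the cut are Φ(±d/2). Power = Φ{[p₁ − p₂ − 1.96√(2 × 0.25/27)] / √[(p₁(1−p₁) + p₂(1−p₂))/27]}.
- d = 0.762: proportions 0.648 and 0.352, power 59.2%. Loss 80 − 59.2 = 20.8 points.
- d = 0.882: proportions 0.670 and 0.330, power 71.9%. Loss 90 − 71.9 = 18.1 points.

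As a cross-check, a median split has efficiency 2/π, which multiplies the noncentrality by 0.798. Φ(0.798 × 2.802 − 1.96) = 60.8% and Φ(0.798 × 3.242 − 1.96) = 73.4%, losses of 19.2 and 16.6 points. Moving the cut to the 75th percentile costs about 29-30 points, and to the 90th about 49-53.

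**Step 3. The Mantel-Haenszel test itself.** Simulation with 26 and 27 patients, two strata unrelated to outcome and a normal outcome, against a linear model with group and stratum. Ranges are across repeat runs.

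| Analysis | 80% planned | 90% planned |
|---|---|---|
| Linear model, outcome uncut | 77-79% | 88-89% |
| Mantel-Haenszel, midpoint cut | 59-62% | 73-74% |
| Mantel-Haenszel, 20% of controls respond | 55-58% | 69-70% |
| Mantel-Haenszel, 10% of controls respond | 46-47% | 60-61% |

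With a median cut, two or three strata, and stratifiers from unrelated to moderately related (correlation 0 to 0.5), the loss ran from 0.875 − 0.738 = 13.7 points to 0.848 − 0.626 = 22.2 points, that is, about 14-22. With the continuity-corrected statistic it was about 29-35 points in the same settings.

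**Step 4. Dependence on normality.** The midpoint comparison was repeated at the same SD with heavy-tailed outcomes, under the 80% assumption. For a t distribution with 3 degrees of freedom the linear model had 83% power and Mantel-Haenszel 92%. For a Laplace distribution the figures were 78-79% and 88-89%. The direction reverses.

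**The case against.** The strongest reply is that this is a supplementary analysis in a randomised trial whose main contrast does not need it. That stands. A reader might infer that the trial loses 14-22 points of power. It does not: the t-test, Mann-Whitney and repeated-measures ANOVA keep the outcome whole.

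Other stronger readings also fail:
- **Every outcome must be cut.** The 1-10 compliance score is already ordered and could enter an extended Mantel-Haenszel test uncollapsed, although the SAP names no such version. Nor is every stratifier arbitrary: the inclusion criteria supply stages G3a, G3b and G4.
- **Crude and adjusted results could not be compared.** They could. A crude odds ratio, with the planned chi-square or Fisher test, can be set beside the pooled odds ratio for the same cut outcome. What cannot be read directly is a pooled odds ratio against the main mean difference, and the SAP does not say that this will be done.
- **The loss is certain and general.** It depends on approximate normality, on assumed power, and on HbA1c alone. No effect size is given for eGFR or compliance, and the SAP itself allows for non-normal data.

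It can also be said that the sentence names no outcome, so applying it to the primary outcomes is an inference. If only naturally categorical outcomes were meant, the plan does not say so, and the primary outcomes then have no method for these variables. Prespecified cut points and strata would remove the post hoc choice, but not the change of scale or the loss of information.

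**Conclusion.** The point holds for the supplementary stratified analysis of the two primary outcomes. As written, the method cannot be applied to change in HbA1c or eGFR without a cut that the plan neither gives nor justifies, and a full-scale alternative is readily available.

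For HbA1c the cost at a midpoint cut is about 14-22 points of power: roughly 77-78% down to 60-62% if 27 per group was set for 80% power, or 89% down to 73% if set for 90%. This rests on the assumed power, the SD back-solved from it, and an approximately normal outcome. Off-centre cuts and the continuity correction make it worse. Heavy tails with a central cut can remove or reverse it. No figure is claimed for eGFR, for compliance or for the power of an interaction test. The mismatch between method and outcome does not depend on any of these assumptions.

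**What to change.** Replace the sentence in the Statistical Analysis Plan section with wording such as:

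> For change in HbA1c and change in eGFR, the influence of other variables will be examined with a linear model on the original scale containing group and the pre-randomisation variable (continuous variables kept uncut), reporting the adjusted mean difference and 95% CI; interaction will be examined by adding a group-by-variable term. Contingency tables and Mantel-Haenszel will be used only for outcomes that are categorical by nature.

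Analyse the compliance score uncollapsed, with an ordinal or linear model. List the variables to be examined; the replacement wording does not supply that list. It also does not cover variables arising after randomisation, so if these are meant by intervening, the plan should say so separately.

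The cost is a short SAP edit, with no new patients or data, and the named SPSS package fits the model. The small downside is reliance on linear-model assumptions. Residuals should be checked and, if they are markedly non-normal, a rank-based or robust version used.

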Clinical study protocol

Effect of the Teleconsultation of Renal Nutrition on Renal Function and Glycemic Control in Patients With DKD

Protocol number: NCT03344549

Date: 30 october 2022

INTRODUCTION

Diabetic kidney disease (DKD) is the leading cause of end-stage renal disease(1). The progression of diabetic nephropathy can be delayed by optimal glycemic control. Nutritional therapy with sugar control and low protein diets (0.8 g/kg/day) are the most recommended (2) however, it is difficult to achieve compliance (3). The dimensions of chronic kidney disease show it as a public health problem that requires the creation of new interventional and educational programs (4). Telehealth may improve clinical outcomes, care coordination, engagement, and satisfaction.

METHODS

Primary objective

The main goal of the study, a randomized and controlled study, is to determine a difference between the nutritional intervention through teleconsultation and the face-to-face consultation in patients with diabetic kidney disease in stage G3a, G3b and G4.

Study design

The trial will be a prospective, randomized, open, controlled design that will last 4 months. The trial was registered in the clinicaltrials.gov registry (ClinicalTrials.gov identifier: NCT03344549).

Study population

A total of 53 adult volunteers with a diagnosis of DKD will be recruited for this study. To be eligible in the trial, subjects must fulfil all of the inclusion criteria and none of the exclusion criteria, as stated below.

The following inclusion criterio will be adopted:

- (1) Outpatients aged 18–80 years.
- (2) With DKD with eGFR <60 ml / min / 1.73m² and ≥ 15 ml / min / 1.73m², (stage G3a, G3b and G4 respectively).
- (3) Written informed consent to participate in this study before any study-mandated procedure.
- (4) Who have access to the internet and have a computer, tablet or smartphone.
- (5) A willingness and motivation to follow the study protocol.

The exclusion criteria will be as follows:

[figure not shown]
- (1) Outpatients who have received prior nutritional treatment for the control of diabetic kidney disease.
- (2) The use of food supplements and / or keto analogues.
- (3) Diagnosis of anemia or recent transfusions (in the last 3 months).
- (4) With serious complications (chronic infection, septicemia, cancer, HIV, Alzheimer's, uncontrolled heart failure, liver failure, refractory arterial hypertension, etc.).

[figure not shown]

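### Two unranked primary outcomes are each tested at 0.05 with no multiplicity or decision rule; if either can carry the claim, familywise error is 7–10% rather than 5%

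*Combined protocol and SAP*

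**What the plan says.** Four places bear on this point.

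- **Primary objective.** There is one aim, "to determine a difference between the nutritional intervention through teleconsultation and the face-to-face consultation in patients with diabetic kidney disease". It names no outcome.
- **Data analysis principles.** Under that same purpose, "the following changes from the baseline (I1) to the end of the study (I6) will be determined as primary outcomes". Two items follow: change in eGFR, then change in HbA1c. They are numbered, but neither is said to lead.
- **Sample size calculation.** The size of 27 per group was reached "considering an expected difference in the Glycated Hemoglobin percentage of 0.7". No planning difference is given for eGFR, and neither an SD nor a target power is stated.
- **Statistical analysis plan.** One threshold covers every comparison: "All tests were two-tailed, and a p value less than 0.05 were considered significant".

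No section contains an alpha split, a hierarchy, a multiplicity adjustment or a rule on whether one or both primary outcomes must be significant.

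**The concern.** With one objective, two primary outcomes and a full 0.05 for each, a reader cannot tell what result would make the trial positive. As written, a significant difference in eGFR alone, or in HbA1c alone, could be reported as the difference the trial set out to find. The 5% the plan implies then applies to each test separately and not to the trial's main claim. A trial with no true effect on either outcome would have close to twice the intended chance of yielding a primary finding.

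**Working it through.** **Inputs from the documents.** Two primary outcomes (Data analysis principles); two-sided 0.05 for each (Statistical analysis plan); HbA1c difference 0.7, planned 27 per group, allocation 26 and 27 (Sample size calculation; Randomization).

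**Assumed, because the documents do not give them.** The correlation r between the two test statistics, the SD of HbA1c, the target power, and any eGFR effect.

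**1. The plan's own figure.** The 27 per group cannot be confirmed without an SD and a power. It can be inverted. From n = 2(z₀.₉₇₅ + z_power)² SD² / d², with n = 27 and d = 0.7:

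- 80% power: SD = 0.7 × √(27 / (2 × (1.960 + 0.842)²)) = 0.918
- 90% power: SD = 0.7 × √(27 / (2 × (1.960 + 1.282)²)) = 0.793

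These SDs are used only to price the remedy in step 4. The error calculation does not depend on them.

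**2. Familywise error if either outcome suffices.** For independent tests, 1 − 0.95² = 0.0975. The upper bound at any correlation is 0.05 + 0.05 = 0.10. For correlated tests, P(|Z₁| > 1.96 or |Z₂| > 1.96) under a bivariate normal gives the middle column below. Simulated t-tests at 26 versus 27 agree (9.7% at r = 0, 9.6% at 0.3, 9.1% at 0.5, 7.0% at 0.9).

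**3. The same quantity under Holm.** When neither outcome has an effect, Holm errs only if the smaller p-value is below 0.025. At r = 0 this is 1 − 0.975² = 0.0494.

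| r (assumed) | Each at 0.05 | Holm |
|---|---|---|
| 0 | 9.75% | 4.94% |
| 0.3 | 9.51% | 4.84% |
| 0.5 | 9.07% | 4.65% |
| 0.7 | 8.35% | 4.30% |
| 0.9 | 7.04% | 3.62% |

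**4. Power cost for HbA1c under Holm.** HbA1c is rejected if its p-value is below 0.025, or if it lies between 0.025 and 0.05 and eGFR has passed at 0.025. With uncorrelated tests:

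power = P₀.₀₂₅ + (P₀.₀₅ − P₀.₀₂₅) × P(eGFR passes at 0.025).

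Noncentral-t power at 26 versus 27 for a difference of 0.7 is 0.777 at 0.05 and 0.679 at 0.025 (SD 0.918), and 0.883 and 0.813 (SD 0.793).

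- *No eGFR effect* (eGFR passes with probability 0.025): 0.679 + 0.098 × 0.025 = 0.681, down from 0.777; and 0.813 + 0.070 × 0.025 = 0.815, down from 0.883. The losses are 9.6 and 6.8 percentage points.
- *eGFR effect of 0.785 SD*, which alone has 80% power at 0.05 and about 71% at 0.025: 0.679 + 0.098 × 0.71 ≈ 0.75; and 0.813 + 0.070 × 0.71 ≈ 0.86.

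**5. If both outcomes must be significant.** A false claim then requires at least one true null to be rejected at 0.05, so the error is at most 5% in any configuration and no adjustment is needed.

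**The case against.** The strongest reply is that these are two questions and not one. The study title names renal function and glycemic control separately, and the outcome list labels each by its own domain. If each is reported as its own claim, whether familywise control is needed is a matter of convention. That reading is open, but the plan does not adopt it: there is a single objective, and both outcomes are introduced as the means of settling it. If two separate claims were intended, the plan should say so.

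It can also be said that HbA1c is the real primary outcome, since the trial was sized on it. Sizing is not ranking, however. eGFR is listed first and both are called primary.

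Three narrower points stand as qualifications.

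- The lower end of the 7–10% range needs a correlation near 0.9, which nothing in the documents supports. Up to 0.5 the figure stays at 9.1–9.75%.
- The 10% ceiling assumes one valid 5% test per outcome. The plan lets a Shapiro–Wilk result choose between the t-test and Mann–Whitney, and also mentions repeated-measures ANOVA for variables measured more than once, so the ceiling covers two fixed tests and not every analysis the plan allows.
- The power figures rest on back-solved SDs and on all 53 participants being analysed, although the protocol lists reasons for discontinuation.

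Finally, if outcome data have already been seen, any rule adopted now may be post hoc, including a choice between Holm and requiring both. Disclosure of timing is therefore part of the fix.

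**Conclusion.** The concern holds and should be fixed. The plan allows either of two unranked primary outcomes to be declared significant at 0.05 and gives no rule for the overall claim. If either can carry that claim, familywise error is 9.75% under independence, 7.0% at an assumed correlation of 0.9, and at most 10% with one valid 5% test per outcome. The inflation depends on that either-outcome reading, which the text permits but does not state. A both-required rule would remove it, and the plan does not state that either. The finding does not depend on the sample size, the SD or the target power.

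**What to change.** Keep both primary outcomes and replace the blanket threshold, for these two only, with Holm: compare the smaller p-value with 0.025 and, only if it passes, compare the other with 0.05. State that either outcome can support the claim under this rule. If the intent is that both must be significant, say that instead and leave alpha unadjusted. A fixed sequence starting with HbA1c is acceptable only if it is set before outcome data are seen.

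In every case, the report should say when the rule was fixed relative to access to outcome data. The document carries "Date: 30 october 2022" and is partly in the past tense, so the trial may have been well advanced or finished by then. A rule that orders the outcomes or demotes one could then be post hoc; Holm avoids choosing an order and uses only one p-value per outcome.

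The cost is one paragraph in the analysis plan and one disclosure sentence, with no new data. When only one outcome has an effect, its power falls by about 7 to 10 percentage points. For HbA1c that is 78% to 68% if 27 per group was set for 80% power, or 88% to 82% if set for 90%, both under the assumed SDs. The loss is smaller when both outcomes have an effect.
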